10.10 APPENDIX 10: ABBREVIATIONS

ADA:	antidrug antibodies
AE:	adverse event
AESI:	adverse event of special interest
ALT:	alanine aminotransferase
C1s:	complement component 1, s subcomponent
CAD:	cold agglutinin disease
COVID-19:	coronavirus disease 2019
CRF:	case report form
CTCAE:	Common Terminology Criteria for Adverse Events
DTP:	direct to patient
ECG:	electrocardiogram
eCRF:	electronic case report form
EOS:	end of the study
FIH:	first-in-human
GCP:	Good Clinical Practice
GDPR:	General Data Protection Regulation
GLP:	Good Laboratory Practice
HCV:	hepatitis C virus
HIV:	human immunodeficiency virus
HRT:	hormonal replacement therapy
IB:	investigator's brochure
ICH:	International Council for Harmonisation
IEC:	Independent Ethics Committee
IMP:	investigational medicinal product
IRB:	institutional review board
ITP:	immune thrombocytopenia
IV:	intravenous

IVIg:	intravenous immunoglobulin
PCSA:	potentially clinically significant abnormality
PCV13:	13-valent pneumococcal
PD:	pharmacodynamics
PK:	pharmacokinetics
PPSV23:	23-valent pneumococcal
PT:	prothrombin time
SAE:	serious adverse events
SAP:	statistical analysis plan
SARS-CoV-2:	serious acute respiratory syndrome coronavirus 2
SC:	subcutaneous
SLE:	systemic lupus erythematosus
SoA:	schedule of activities
SOC:	system organ class
SUSAR:	suspected unexpected serious adverse reactions
TEAE:	treatment-emergent adverse event
TESAE:	treatment-emergent serious adverse event
ULN:	upper limit of normal
WBC:	white blood cells

10.11 APPENDIX 11: PROTOCOL AMENDMENT HISTORY

This is the third amendment of the protocol. Changes to the protocol for amended protocol 03 are summarized before the Table of Contents. Changes to the protocol for amended protocols 01 and 02 are summarized in this section.

Amended protocol 02 (10 December 2020)

This amended protocol 02 (Amendment 02) is considered to be substantial based on the criteria set forth in Article 10(a) of Directive 2001/20/EC of the European Parliament and the Council of the European Union.

OVERALL RATIONALE FOR THE AMENDMENT

Changes in the protocol have been implemented to address requests received from the US Food and Drug Administration as well as additional corrections and clarifications.

PROTOCOL AMENDMENT SUMMARY OF CHANGES

Section # and Name	Description of Change	Brief Rationale
1.3 Schedule of activities	Pre-dose weight added on Day 1	Weight needed for loading dose
1.3 Schedule of activities, footnote g;	Titers may not be used in lieu of documentation of prior vaccination	Clear titer cutoffs associated with protection do not exist for most of the required vaccines
8.2.6 Vaccinations against encapsulated bacteria		
5.1 Inclusion criteriion I03	For participants who have not previously received sunitlimab, one of their prior treatments must have been a thrombopoietin receptor agonist	US FDA request
6.8 Concomitant therapy	Clarification that vaccinations, such as the seasonal influezna vaccine, are permitted during the study	Clarification
6.8.1 Rescue medicine	Clarification that a dose increase in a concomitant ITP medication is considered rescue therapy	Clarification
8.2.4.1 Additional testing in case of hypersensitivity/allergic reaction	Clarification of testing to be performed in case of hypersensitivity/allergic reaction	Some of the lab tests listed in the prior version were difficult to perform and of unclear utility
8.3.1 Time period and frequency for collecting AE and SAE information	Additional information for participants transitioning from study TDR16218	For these participants there are additional requirements and considerations for AE/SAE reporting
10.1.9 Study and site start and closure	Addition of a dosing and enrollment hold for toxicity	US FDA request
10.2 Appendix 2: Clinical Laboratory Tests	Thrombopoietin removed from clinical chemistry panel	Test not essential for study and cannot be performed through the central lab
Throughout	Additional clarifications and corrections to typography and formatting	Clarification and consistency with document standards

Amended protocol 01 (08 December 2020)

Changes for amended protocol 01 (08 December 2020) were considered to be substantial based on the criteria set forth in Article 10(a) of Directive 2001/20/EC of the European Parliament and the Council of the European Union.

OVERALL RATIONALE FOR AMENDMENT 01

Changes in protocol amendment 01 were implemented to address requests received in a Voluntary Harmonisation Procedure communication.

PROTOCOL AMENDMENT 01 SUMMARY OF CHANGES

Section # and Name	Description of Change	Brief Rationale
1.1 Synopsis, Overall design; 1.3 Schedule of activities, footnote e; 2.3 Benefit/Risk assessment; 4.1 Overall design; 4.2 Scientific rationale for study design	Addition of a maximum duration of treatment of 104 weeks per participant, and also noted long-term safety profile for sunitimlimab, another compound with a similar mechanism of action.	Added limit as a safety measure, and added further information to support likelihood of long-term safety
1.1 Synopsis, Overall design; 4.1 Overall design, 6.1.2 Subcutaneous dose administration	Specified that participants should be observed for 30 minutes after IMP administration for the first 6 SC administrations	Additional safety monitoring
1.1 Synopsis, Data Monitoring/Other committee; 10.1.5 Review Committees	Added mention of Data Monitoring Committee to synopsis, renamed "Data Monitoring Committee" subheading as "Study Monitoring Committee," and added a brief description of the Data Monitoring Committee, which will include at least 2 investigators participating in the study	Increased safety monitoring
1.3 Schedule of activities; 5.1 Inclusion criterion I05	Male and female participants are now required to continue contraception until 52 weeks after the last dose of BIVV020. A urine pregnancy test was added to the End of Study visit for women of child-bearing potential.	Required contraception extended due to the prolonged half-life of BIVV020
6.1 Study interventions administered (new subsections 6.1.2 and 6.1.3)	Additional details for IMP administration added	Health authority request
6.2 Preparation/handling/storage/accountability	Added statement referring to the Pharmacy Manual for procedure details	Clarification
6.8 Concomitant therapy	Clarification that thrombopoietin agonists may be restarted by the Investigator after BIVV020 administration if a participant has an insufficient response to BIVV020	Clarification
new section added: 7.1.5 Thrombocytosis; subsequent subheadings renumbered	A new section was added to specify that BIVV020 should be discontinued if platelet counts rise above $450 \times 10^9/L$	Added guidance for thrombocytosis
10.1.1 Regulatory and ethical considerations	Clarification that the Declaration of Helsinki guidelines referenced are the most recent guidelines from 2013	Clarification

[figure not shown]
Section # and Name	Description of Change	Brief Rationale
10.4.2 Contraceptive guidance	Double-barrier contraception removed as a highly effective contraceptive method	Double barrier contraception is not considered to be highly effective as per the Clinical Trial Facilitation Group

## VERSION HISTORY

This statistical analysis plan (SAP) for study PDY16894 is based on the protocol dated 25-Jan-2021. There are no major changes to the statistical analysis features in this SAP. The first participant was enrolled on 15 Feb 2021. The SAP is approved before the first interim analysis is conducted.

## 1 INTRODUCTION

### 1.1 STUDY DESIGN

This is a Phase 2a, open-label, non-randomized, multicenter study to evaluate the efficacy, safety and tolerability of BIVV020 in adults with persistent/chronic primary ITP.

During the 56-day screening period, prospective participants will have a detailed medical history documented, physical evaluations and blood samples (including platelet count) collected. For participants receiving sutmilimab (BIVV009) in study TDR16218, they may continue to receive sutmilimab during screening, until at least 14 days prior to the first administration of investigational medicinal product (IMP) - BIVV020.

The study will enroll approximately 12 participants: up to 6 participants who have received and responded to sutmilimab (BIVV009) in study TDR16218 (switchers), as well as patients who have not previously received sutmilimab (naïve participants).

A loading dose of BIVV020 at 50 mg/kg intravenous (IV) will be administered on Day 1, followed by maintenance doses of 600 mg subcutaneous weekly starting on Day 8 until the last participant enrolled has completed 52 weeks of treatment. The maximum duration of treatment for a participant is 104 weeks.

The on-site visits will be conducted weekly from Week 1 to Week 6, biweekly from Week 7 to Week 12, every 4 weeks from Week 13 to Week 24, every 8 weeks after Week 24 until the end-of-study (EOS) visit. Platelet counts will be collected during the on-site visits.

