1.3 SCHEDULE OF ACTIVITIES (SOA)

	Screening/Transition period ^a	Loading dose		Weekly maintenance dosing										End of study	
				Weekly clinic visits					Visits every 2 weeks		Visits every 4 weeks		Visits every 8 weeks (minimum)		
Week	0				1-6					7-12 ^c		13-24 ^d		25+ ^e	
Day	D-56 to D-1	D1	D1	D1	D4 ^b	D8	D15	D22	D29	D36	D43	D44 - D85	D86 - D169	D170+	
Hour		0H	1H	4H											
Window					±1 d	±1 d	±1 d	±1 d	±1 d	±1 d	±1 d	±2 d	±3 d	±4 d	±14 d
Informed consent	X														
Inclusion and exclusion criteria ^f	X														
Demography	X														
Medical history	X														
Immunization review/ vaccination ^g	X														
Past and current medical conditions	X														
ECOG status	X														
HIV, hepatitis B and C, and SARS-CoV-2 testing ^h	X														
FSH (if applicable) ⁱ	X														
Serum creatine kinase	X														

	Screening/Transition period ^a	Loading dose		Weekly maintenance dosing									End of study		
				Weekly clinic visits						Visits every 2 weeks	Visits every 4 weeks	Visits every 8 weeks (minimum)			
Week		0				1-6						7-12 ^c	13-24 ^d	25+ ^e	
Day	D-56 to D-1	D1	D1	D1	D4 ^b	D8	D15	D22	D29	D36	D43	D44 - D85	D86 - D169	D170+	
Hour		0H	1H	4H											
Window					±1 d	±1 d	±1 d	±1 d	±1 d	±1 d	±1 d	±2 d	±3 d	±4 d	±14 d
Full physical examination including height and weight ⁱ	X														X
Weight (predose)	X														
Serum pregnancy test (WOCBP only)	X														
Urine pregnancy test (WOCBP only)		X								X		X ^k	X	X	X
IMP administration ^l															
BIVV020 50 mg/kg IV		X													
BIVV020 600 mg SC						X ^m	X	X	X	X	X	X ⁿ	X	X	
Safety assessments															
Vital signs ^o	X	X	X	X	X	X	X	X	X	X	X	X	X	X	X
Abbreviated physical exam ^p		X							X			X ^k	X	X	

	Screening/Transition period ^a	Loading dose		Weekly maintenance dosing									End of study		
				Weekly clinic visits						Visits every 2 weeks	Visits every 4 weeks	Visits every 8 weeks (minimum)			
Week		0				1-6						7-12 ^c	13-24 ^d	25+ ^e	
Day	D-56 to D-1	D1	D1	D1	D4 ^b	D8	D15	D22	D29	D36	D43	D44 - D85	D86 - D169	D170+	
Hour		0H	1H	4H											
Window					±1 d	±1 d	±1 d	±1 d	±1 d	±1 d	±1 d	±2 d	±3 d	±4 d	±14 d
Hematology, chemistry, coagulation, and urinalysis ^q	X	X					X		X			X ^k	X ^r	X	X
SLE panel ^q	X								X			X ^k	X	X	X
12-lead ECG	X					X									X
AE review	X	X			X	X	X	X	X	X	X	X	X	X	X
Concomitant medication review		X	X	X	X	X	X	X	X	X	X	X	X	X	X
Local site reactions ^s					X	X	X	X	X	X	X	X	X	X	

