Participant diary ^t												X	X	X	
Phone calls ^u												X	X	X	X
Pharmacodynamics ^v															
Platelets ^w				X	X	X	X		X		X	X	X	X	X

	Screening/Transition period ^a	Loading dose		Weekly maintenance dosing								End of study			
				Weekly clinic visits					Visits every 2 weeks	Visits every 4 weeks	Visits every 8 weeks (minimum)				
Week		0				1-6					7-12 ^c	13-24 ^d	25+ ^e		
Day	D-56 to D-1	D1	D1	D1	D4 ^b	D8	D15	D22	D29	D36	D43	D44 - D85	D86 - D169	D170+	
Hour		0H	1H	4H											
Window					±1 d	±1 d	±1 d	±1 d	±1 d	±1 d	±1 d	±2 d	±3 d	±4 d	±14 d
BIVV020 dosing schedule															
Archival PD sample		PX00	PX01			PX02			PX03			PX04 ^y	PX05 ^r	PX06+	X
DNA sample for future research ^x		X													
Pharmacokinetics/ADA ^v															
BIVV020 plasma samples		P00	P01			P02	P03		P04		P05	P06 ^y	P07 ^r	P08+	X
Anti-BIVV020 antibodies		PD00							PD01			PD02 ^y	PD03 ^r	PD04+	X ^z

- ^a The Transition Period applies only to participants who were previously receiving sutimlimab, and is a period of at least 14 days between the last sutimlimab dose and the first dose of BIVV020. This period is included as part of the Screening Period.
- ^b The Day 4 visit may be performed at the participant's home using a home nursing service.
- ^c Visits will occur at Weeks 8, 10, and 12.
- ^d Visits will occur at Weeks 16, 20, and 24.
- ^e Visits will occur at Weeks 32, 40, 48, etc, with phone calls occurring approximately 4 weeks after each visit. Participants will continue to receive BIVV020 until the last participant enrolled has completed 52 weeks of treatment. For the last participant enrolled, a visit should occur at Week 52. Visits should occur around the time a participant is transitioning off BIVV020, even if this visit is less than 8 weeks from the prior visit. The maximum duration of treatment for an individual participant is 104 weeks.
- ^f Inclusion and exclusion criteria should be reviewed on Day 1 prior to enrollment.
- ^g Participants should have documented vaccination against encapsulated bacterial pathogens (*Neisseria meningitidis*, including serogroup B meningococcus [where available]), *Haemophilus influenzae*, and *Streptococcus pneumoniae*) within 5 years prior to enrollment. The participant should receive the vaccine series as early as possible. See [Section 8.2.6](#) for additional details.

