- ^h Testing includes HBsAg, HBcAb (IgG and IgM), anti-HCV Ab, and HIV test. Need for SARS-CoV-2 testing to be determined for each site. If SARS-CoV-2 testing is performed, a molecular test should be used.
- ⁱ FSH testing should be performed in participants with at least 12 months of amenorrhea. See [Section 10.4.1](#).

- j* Height at screening only.
- k* To be performed at Weeks 8 and 12 only.
- l* In addition to the IMP being dispensed in the clinic, the IMP may be dispensed for home administration via DTP services, except if prohibited by local regulatory authorities.
- m* Injections will be administered by site staff at visits that occur during Weeks 1 to 5. Participants will perform the injection in the clinic on Week 6 under the supervision of study staff.
- n* At visits that occurs from Week 7 onward, injections will be performed in the clinic by the participants, under the supervision of study staff.
- o* See [Section 8.2.2](#).
- p* See [Section 8.2.1](#). Ad-hoc physical exams may be performed at the discretion of the Investigator based on any AEs reported by the participant.
- q* See [Section 10.2](#) for a list of tests to be performed. Labs should be performed prior to drug administration.
- r* To be performed at Week 24 only.
- s* See [Section 8.2.7](#).
- t* Participants will record IMP administrations in a paper or e-diary when performing administrations at home.
- u* Phone calls will be performed to remind participants to take their injections, answer any questions they may have regarding the injections, and to assess AEs. From Weeks 7 to 24, phone calls will be performed on weeks that the participants are not seen in the clinic (Weeks 7, 9, 11, 13 to 15, 17 to 19, and 21 to 23). After Week 25, phone calls will be performed approximately 4 weeks after each previous visit. (If a visit during this period occurs within approximately 4 weeks of the prior visit, a phone call is not necessary.) Phone calls should continue to occur approximately every 8 weeks after the cessation of treatment, until the EOS visit.
- v* To be performed prior to drug administration unless otherwise noted.
- w* Platelet count should not be performed as a separate test at visits when a complete blood count is performed.
- x* If participant provided consent for future research.
- y* To be performed at Week 12 only.

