### **4.3 PRIMARY ENDPOINT(S) ANALYSIS**

The primary endpoint is the proportions of participants who met the following criteria:

1. For naïve participants,
  - a platelet count  $\geq 50 \times 10^9/L$  OR
  - a  $\geq 20 \times 10^9/L$  increase from baseline if baseline platelet count  $< 15 \times 10^9/L$  at  $\geq 50\%$  of scheduled visits from Week 3 to Week 24.

For switchers, a platelet count  $\geq 30 \times 10^9/L$  at  $\geq 50\%$  of scheduled visits from Week 3 to Week 24.

2. No concomitant ITP therapy from Week 3 to Week 24.

Concomitant medications are defined in [Section 5.3](#). The ITP therapies will be identified by the Sanofi coding group, reviewed by medical, and defined in the programming specifications. The ITP therapies include corticosteroids, thrombopoietin receptor agonists, intravenous immunoglobulin, anti-D immunoglobulin, rituximab, fostamatinib, immunosuppressants (azathioprine, cyclosporin A, mycophenolate mofetil), cyclophosphamide, dapsone, danazol.

The response rate will be summarized for naïve participants, switchers, and total for the ITT along with the 95% exact Clopper-Pearson Confidence Interval (CI).

Platelet counts will be summarized by visit. These plots will also be provided:

- Individual platelet count profile: line plot of platelet count by visit for each participant

- Spaghetti plot platelet count by participant
- Median platelet count/change from baseline with by visit

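### The primary endpoint's 50% rule has no stated denominator: ten clinic visits fall in Weeks 3 to 24, but the schedule of activities plans platelet counts at only eight of them

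*SAP*

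**What the plan says.** **Endpoint.** SAP section 4.3 and the objectives tables of both documents define response by a platelet threshold met at 50% or more "of scheduled visits from Week 3 to Week 24". The threshold differs between naïve participants and those switched from sutimlimab, but the visit rule is the same.

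**Visits.** SAP section 1.1 says "The on-site visits will be conducted weekly from Week 1 to Week 6, biweekly from Week 7 to Week 12, every 4 weeks" up to Week 24. Footnotes to the schedule of activities (protocol section 1.3) fix the later visits: "Visits will occur at Weeks 8, 10, and 12" and "Visits will occur at Weeks 16, 20, and 24". SAP Table 6 lists Day 22 and Day 36 among the scheduled post-baseline visits, each with a window of plus or minus one day.

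**Platelet counts.** SAP section 1.1 adds, with no exception, that "Platelet counts will be collected during the on-site visits". In the protocol's schedule, the platelet row is marked at Days 15, 29 and 43 but blank at Days 22 and 36. The "Hematology, chemistry, coagulation, and urinalysis ^q" row is blank on those two days as well. A footnote to the platelet row says "Platelet count should not be performed as a separate test at visits when a complete blood count is performed". That footnote lets a blood count stand in for the separate test, but no blood count is planned at either visit.

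**Missing counts.** Protocol section 9.3.2 rules out imputation. It treats a participant who stops treatment before Week 3 as a non-responder, and assesses one who stops between Weeks 3 and 24 on the data available. SAP section 5.4 treats a visit with no measurement in its window as missing. Neither says whether such a visit stays in the 50% denominator for a participant who remains on treatment.

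**The concern.** SAP section 1.1 and the protocol's schedule disagree on whether platelets are counted at Weeks 3 and 5, and the endpoint is worded in terms of scheduled visits, not scheduled counts. A programmer who follows that wording would put ten visits in the denominator while the planned data can fill only eight. Every fully observed participant would then face a stricter test than half of the counts actually taken. Another programmer, taking the visits with a count, would use eight. Both could claim to follow the plan, and they would classify the same participant differently on the primary endpoint. With about 12 participants, and results also reported separately for naïve participants and switchers, one reclassification is visible in the headline figure.

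**Working it through.** Neither document prints a denominator, and the sample size is not statistically derived, so there is no figure of the plan's own to reproduce. The check is a count of visits, followed by its effect on one participant.

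**Step 1. Visits and planned counts.** Day = 7 × week + 1. The hematology footnotes limit that panel to Weeks 8 and 12 in the Week 7–12 column and to Week 24 in the Week 13–24 column.

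| Week | Day | Platelet row | Hematology row |
|---|---|---|---|
| 3 | 22 | blank | blank |
| 4 | 29 | marked | marked |
| 5 | 36 | blank | blank |
| 6 | 43 | marked | blank |
| 8 | 57 | marked | marked |
| 10 | 71 | marked | no |
| 12 | 85 | marked | marked |
| 16 | 113 | marked | no |
| 20 | 141 | marked | no |
| 24 | 169 | marked | marked |

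Clinic visits: 10. Visits with a planned count: 8.

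**Step 2. Is the table read correctly?** The platelet, hematology, plasma-concentration and subcutaneous-dosing rows each split into 15 cells for 15 columns. Read with the same column mapping, the plasma-concentration row gives Days 8, 15, 29 and 43 and Weeks 12 and 24, which are the visits that SAP section 4.7 lists. This supports the mapping but does not prove the platelet row.

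**Step 3. What each reading requires.**

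- A. Ten visits, all measured (SAP section 1.1 taken at its word): 0.5 × 10 = 5 of 10.
- B. Eight visits with a planned count: 0.5 × 8 = 4 of 8.
- C. Ten visits in the denominator, only the eight planned counts taken: 0.5 × 10 = 5, out of 8 available, and 5/8 = 62.5%.

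A participant with exactly four qualifying counts out of eight scores 4/8 = 50% under B (responder) and 4/10 = 40% under C (non-responder), other criteria being met.

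**Step 4. Effect on the reported rate.** One participant is 1/12 = 8.3 points overall and 1/6 = 16.7 points in a cohort of six. For example, with Clopper-Pearson 95% intervals, 6/12 = 50.0% (21.1 to 78.9) becomes 5/12 = 41.7% (15.2 to 72.3).

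**Step 5. Where the difference arises (illustration only).** Assume each visit qualifies independently with probability p. Then P(X ≥ k) is the sum over j ≥ k of C(n, j) p^j (1 − p)^(n − j). At p = 0.5: B = 163/256 = 0.637; C = 93/256 = 0.363; A = 638/1024 = 0.623.

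| p | A: 5 of 10 | B: 4 of 8 | C: 5 of 8 |
|---|---|---|---|
| 0.3 | 0.150 | 0.194 | 0.058 |
| 0.4 | 0.367 | 0.406 | 0.174 |
| 0.5 | 0.623 | 0.637 | 0.363 |
| 0.6 | 0.834 | 0.826 | 0.594 |
| 0.7 | 0.953 | 0.942 | 0.806 |

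A and B differ by at most 0.194 − 0.150 = 0.044. Only C departs materially from B, by 14 to 27 points here. The values of p and the independence are assumptions, not figures from the documents.

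**Step 6. Unscheduled counts.** SAP section 5.4 lets an unscheduled measurement fill a visit window. If the denominator is the visits with a count, it could then be 8, 9 or 10 for different participants. With 9, the bar is 4.5, so five are needed. A participant with 4 of 8 and one extra non-qualifying count at Day 22 falls to 4/9 = 44.4%.

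**The case against.** **A sensible programmer would use eight.** A platelet criterion at scheduled visits can be read as visits where a platelet count is scheduled, and protocol section 9.3.2 leans towards available data. Table 6 serves efficacy, safety, PK and ADA together, so listing Days 22 and 36 there does not by itself make them platelet visits. This is fair, and it may be what the sponsor intends. But the available-data rule is written only for participants who stop treatment between Weeks 3 and 24, and nothing extends it to those who stay on.

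**The table was machine-read.** This stands as a caution. Elsewhere in the same table, the row for pre-dose weight has its only mark under screening, although the amendment history speaks of Day 1. The platelet row itself is marked four hours after the start of dosing, although a footnote asks for pre-dose sampling unless noted. Neither shows that the platelet row is shifted, but the two blanks must be confirmed on the source page.

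**Stronger readings that do not hold.**

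- A reader might infer that the SAP and the protocol give materially different response rates because one implies ten visits and the other eight. They do not: if all ten are measured, 5 of 10 and 4 of 8 behave almost alike. The effect needs ten visits in the denominator with counts at only eight.
- A reader might infer that Weeks 3 and 5 can never count as responses. SAP section 5.4 admits unscheduled measurements within the windows, and protocol Appendix 2 permits additional tests.
- A reader might take the gap between 0.637 and 0.363 as the expected distortion. It rests on independent visits and an assumed p. Counts within a participant are likely to be correlated, which would probably leave fewer people at exactly four of eight.
- Opening the window at a visit without a planned count is not in itself a defect; starting in effect at Week 4 is workable.

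**Conclusion.** The point holds as an undefined primary-endpoint denominator, together with an SAP sentence that does not match the protocol's schedule. Taken literally, the rule counts ten visits against eight planned counts and raises the working bar from 50% to 62.5% of measured visits. The participants affected are those with exactly four qualifying counts out of eight; the documents give no basis for saying how many there will be. Each one moves the rate by 8.3 points at 12 participants or 16.7 points in a cohort of six. These figures assume that the two blanks are real, that all eight planned counts are obtained, and that no unscheduled count falls in the Day 22 or Day 36 windows.

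The documents do not support a claim that the response rate will be biased by a particular amount, or that the study is unable to answer its question. It is descriptive and tests no hypothesis. It is still worth correcting, because this proportion is the primary result of an open-label study and the rule that produces it should not be left to the programmer.

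**What to change.** 1. Confirm on the source page of the protocol that the platelet and hematology rows are blank at Days 22 and 36.
2. In SAP section 4.3, define the denominator as the visits with a protocol-scheduled platelet count: Weeks 4, 6, 8, 10, 12, 16, 20 and 24. Four of eight then meets the rule.
3. In the same place, state whether a missed scheduled count stays in the denominator as not qualifying or is removed, for participants who remain on treatment. Removal would match the available-data rule that protocol section 9.3.2 applies to those who stop after Week 3. Also state whether an unscheduled count may stand in for a scheduled one, and that a count near Day 22 or Day 36 does not add a visit to the denominator.
4. Correct SAP section 1.1 so that it says counts are taken at the visits marked in the schedule.
5. While editing, check the Week 10 window. Table 6 targets day 80 ± 2, but 7 × 10 + 1 = 71. If these windows are applied to the primary endpoint, an on-time Week 10 count would be lost and seven usable counts would remain.

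Do not add draws at Days 22 and 36. The SAP records that the first participant was enrolled on 15 Feb 2021, so a mid-study change would give earlier and later participants unequal denominators. The cost is a few sentences in the SAP, with no new data and no change to visits.
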